4.2.2. Adherence to Study Drug

The total number of doses administered will be summarized using descriptive statistics for each study drug.

The presumed total number of doses administered to a subject will be determined by the data collected on the drug accountability CRF using the following formula:

Total Number of Doses Administered =

$$\left(\sum \text{No. of Doses Dispensed} \right) - \left(\sum \text{No. of Doses Returned} \right)$$

If a bottle is dispensed and returned empty, then the number of tablets returned will be entered as zero. If a bottle is dispensed but not returned (missing) then the number of tablets from that bottle will be counted as zero.

If calculated adherence is greater than 100%, the result will be set to 100%.

The adherence will be calculated separately for each treatment administered: filgotinib 200 mg/PTM or lanraplenib 30 mg/PTM. The overall adherence will be lowest of the two.

4.2.2.1. Prescribed Adherence

The level of prescribed adherence to the study drug regimen will be determined by the total amount of study drug administered relative to the total amount of study drug specified by the protocol for a subject who completes treatment in the study.

The level of prescribed adherence will be expressed as a percentage using the following formula:

$$\text{Prescribed Adherence (\%)} = \left(\frac{\text{Total Amount of Study Drug Administered}}{\text{Total Amount of Study Drug Specified by Protocol}} \right) \times 100$$

Descriptive statistics for the level of prescribed adherence up to Week 12, up to Week 24 and the entire study duration with the number and percentage of subjects belonging to adherence categories: < 80, ≥ 80% will be provided by treatment group for the Safety Analysis Set.

The expected amount of study drug to be administered is derived as:

- up to Week 12 is 84 (7 * 12) doses
- up to Week 24 is 168 (7 * 24) doses
- Entire study is 336 (7 * 48) doses

The total amount of study drug administered up to week 12/24 will be calculated based on the drug accountability reported on CRF: (total pills dispensed – total pills returned) up to Week 12/24 visit.

No formal statistical testing is planned.

By-subject listings of study drug administration and accountability will be provided separately by subject ID number in ascending order and in chronological order for each treatment separately.

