3.3. Study Treatments

Eligible subjects will be randomized 2:2:1 in a blinded fashion to 1 of 3 arms and receive daily oral doses of the following study drugs starting on Day 1 for 12 weeks:

Arm	Study Drugs			
Filgotinib 200 mg (n=20)	filgotinib 200 mg + PTM GS-9876 30 mg			
GS-9876 30 mg (n=20)	GS-9876 30 mg + PTM filgotinib 200 mg			
Placebo (n=10)	PTM filgotinib 200 mg + PTM GS-9876 30 mg			

PTM = placebo to match

On Day 1, randomization will be stratified by two factors: (i) disease subtype (CCLE [eg DLE] vs SCLE) and (ii) concurrent background DMARD use vs no use.

At Week 12, upon completion of all scheduled assessments, subjects on placebo will be re-randomized 1:1 to receive filgotinib 200 mg + PTM GS-9876 30 mg once daily or GS-9876 30 mg + PTM filgotinib 200 mg once daily for the remainder of the study in a blinded fashion. Dosing and assessments for all subjects will continue through Week 24.

Subjects who have not permanently discontinued study drug dosing in the first 24-week period may enter the subsequent 24-week extension period where they will continue to receive their assigned dose of study drug, in a blinded fashion.

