3.6. End of Study

End of study is defined as when the last subject has completed 24 weeks of dosing (or 48 weeks of dosing if entering the extension period) plus the FU visit 4 weeks after the last dose of study drug (if applicable).

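### The 336-dose denominator for entire-study adherence is wrong for subjects who complete 24 weeks and do not enter the optional extension: full adherence is reported as 50% and classed below 80%

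*SAP*

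**What the plan says.** SAP 4.2.2.1 defines prescribed adherence as the amount of drug administered divided by the "total amount of study drug specified by the protocol for a subject who completes treatment in the study". It then fixes the expected amounts for three periods: "up to Week 12 is 84 (7 * 12) doses", "up to Week 24 is 168 (7 * 24) doses" and "Entire study is 336 (7 * 48) doses". No condition is attached to the last figure. Results are shown as descriptive statistics and in "adherence categories: < 80, ≥ 80% will be provided by treatment group for the Safety Analysis Set". That set is everyone who took at least one dose (SAP 3.1.3), so it includes subjects who never enter the extension.

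The numerator is doses dispensed minus doses returned. SAP 4.2.2 puts it this way: "The presumed total number of doses administered to a subject will be determined by the data collected on the drug accountability CRF".

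On the length of the course, Protocol 3.3 says that subjects still on drug after the first 24 weeks "may enter the subsequent 24-week extension period", and Protocol 3.4 gives 48 weeks as a maximum. Protocol 3.6 defines the end of study by 24 weeks of dosing, "or 48 weeks of dosing if entering the extension period".

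**The concern.** The SAP ties the denominator to what the protocol specifies for a completer, but the protocol describes two completing courses: 24 weeks without the extension and 48 weeks with it. The figure of 336 fits only the second. For a subject who finishes the first, the entire-study row sets the doses taken against doses that were never assigned or dispensed, and reports the gap as non-adherence.

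What is at stake is how that row reads. It would combine a permitted choice not to continue with tablets actually missed, and the 80% cut would put both in the same category. Prescribed adherence is the only adherence percentage defined in SAP 4.2.2, so no on-treatment percentage beside it would separate the two over the whole study.

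**Working it through.** **Inputs**
- One dose of each study drug per day (Protocol 5.5). The rule is applied to each drug separately and the lower result is taken (SAP 4.2.2); the expected count is the same for both.
- Expected doses of 84, 168 and 336, and a cut at 80% (SAP 4.2.2.1).
- Week 24 visit window of ±5 days (Protocol Appendix 2).
- Dispensing at Day 1 and Weeks 4, 8, 12, 16 and 20. Week 24 dispensing is for extension entrants only (Protocol 6.4 and Appendix 2).
- 30 tablets per bottle (Protocol 5.2.2 and 5.3.2).

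**1. Reproduce the SAP's figures.** Expected doses = 7 × weeks: 7 × 12 = 84; 7 × 24 = 168; 7 × 48 = 336. All three agree.

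**2. Establish the course of a non-entrant.**
- Entry is optional and 48 weeks is a ceiling (Protocol 3.3, 3.4).
- Dosing ends at 24 weeks for non-entrants (Protocol 3.6).
- An early termination visit applies to leaving before Week 24, or before Week 48 only for those who entered (Protocol 6.7). Stopping at Week 24 as planned is not early termination.
- No drug is dispensed to them at Week 24.

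Their protocol-specified amount is therefore 168 doses.

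**3. Apply the rule as written.** For a non-entrant who took every dose:
- Entire-study score = 168/336 = 50.0%, classed below 80%.
- Against the subject's own course = 168/168 = 100%, classed at or above 80%.

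**4. Test whether any such subject could reach 80%.**
- Week 24 visit 5 days early: 163/336 = 48.5%. Five days late: 173/336 = 51.5%.
- Upper limit, assuming one bottle of each drug at each of the six dispensings and nothing counted as returned: 6 × 30 = 180, and 180/336 = 53.6%.
- Doses needed for 80%: 0.80 × 336 = 268.8, so 269 doses, or 269/7 = 38.4 weeks.

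No subject who stops at Week 24 as planned can be classed at or above 80%.

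**5. Identify whose category changes.** 0.80 × 168 = 134.4, so 135 doses. A non-entering completer with 135 or more of 168 doses moves from below 80% to at or above 80% when the denominator is corrected. One with fewer is below 80% either way, although the percentage still doubles.

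**6. Effect on a group mean.** If a share p of otherwise fully adherent subjects completes 24 weeks and does not enter, the reported mean is 100(1 − p) + 50p = 100 − 50p. This gives 95% at p = 0.10, 87.5% at p = 0.25 and 75% at p = 0.50. These values of p are assumptions; the documents give none.

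**7. Effect of one subject.** Planned arms are 20, 20 and 10, and placebo is re-randomized 1:1, so about 5 per switched group. One fully adherent non-entrant moves the below-80% share by 1/20 = 5 points and the mean by 50/20 = 2.5 points in an arm of 20. In a group of 5 the shifts are 1/5 = 20 points and 50/5 = 10 points.

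**The case against.** The best defence is that prescribed adherence is meant to measure shortfall from the full planned course, and 48 weeks is the longest course in the protocol. On that view the measure is not purely one of missed doses. A placebo subject who stops at Week 12 cannot exceed about 84/336 = 25%, and that may be intended. This justifies a full-course denominator for someone who stops early. It does not reach a subject who took every dose the protocol assigned, and the SAP nowhere says that declining the extension should count as a shortfall.

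A second defence is that other outputs expose the problem. The Week 24 adherence summary would show the same subject at 100%. Exposure is tabulated through Weeks 24 to 48 (SAP 4.2.1), disposition is reported by period (SAP 4.1), and there are by-subject accountability listings. A careful reader could work out what happened, but the entire-study row itself would still be wrong.

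The limits on impact do stand. No formal testing is planned for this measure. There is no per-protocol analysis (SAP 3.1.4), so the 80% cut excludes no one. Neither estimand uses adherence (SAP 3.9 and Table 4).

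A reader might infer that the misclassified share equals the share not entering the extension. The documents do not support that. Non-entrants also include subjects who stopped drug before Week 24 and are ineligible to enter (Protocol 3.5.2), and completers below 80% on either denominator. A reader might also infer a false adherence difference between randomized arms. That would require extension entry to differ by group, on which the documents are silent. The entire-study tables use five groups (SAP Table 2) and are not the randomized comparison with placebo.

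**Conclusion.** The point holds for a defined group: subjects who complete the 24-week dosing period and do not enter the extension. For them the stated rule contradicts the SAP's own definition of the denominator and halves the percentage. This is a rule that gives a wrong figure, rather than a detail left out.

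The conclusion rests on two readings: that 336 applies to all subjects, since the SAP gives one number and no alternative, and that 24 weeks is the complete course for a non-entrant, which Protocol 3.6 and the dispensing schedule support. The size per subject is certain. The number of subjects is not, because no non-entry rate is given. The matter is worth correcting because the change is so small, but no efficacy or safety conclusion depends on it.

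**What to change.** In SAP 4.2.2.1, make the entire-study denominator conditional: 168 doses for subjects who complete Week 24 dosing and do not enter the extension, and 336 for extension entrants. State also which denominator applies to subjects who discontinue before Week 24. That choice can affect the category of anyone who stops after taking 135 or more doses (135/7 = 19.3 weeks), so it should be written down rather than left to programming.

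Alternatively, replace the entire-study row with a Weeks 24-48 summary restricted to extension entrants, with a denominator of 336 − 168 = 168 doses. The existing Week 12 and Week 24 rows stay as they are.

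The cost is a line or two of SAP text and, for the first option, one conditional in the program. No new data are needed, because extension entry can be identified from Week 24 dispensing.

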4.3. Protocol Deviations

Subjects who did not meet the eligibility criteria for study entry, but enrolled in the study, will be summarized. The summary will present the number and percentage of subjects who did not meet at least 1 eligibility criterion and the number of subjects who did not meet specific criteria by treatment group based on the All Randomized Analysis Set. A by-subject listing will be provided for those subjects who did not meet at least 1 eligibility (inclusion or exclusion) criterion. The listing will present the eligibility criterion (or criteria if more than 1 deviation) that subjects did not meet and the related comments, if collected.

Protocol deviations occurring after subjects entered the study are documented during routine monitoring. The number and percentage of subjects with important protocol deviations by deviation reason (eg, violation of select inclusion/exclusion criteria) will be summarized by treatment group for the Safety Analysis Set. A by-subject listing will be provided for the subjects with important protocol deviations.

5. BASELINE CHARACTERISTICS

5.1. Demographics

Subject demographic variables will be summarized by treatment group and overall using descriptive statistics for continuous variables, and using number and percentage of subjects for categorical variables. The summary of demographic data will include the following:

- age (on the first dose date of any study drug) as a continuous variable
- age group (< 50, \geq 50 years)
- race
- ethnicity (Hispanic or Latino, not Hispanic or Latino)

Subject demographic variables (i.e., age, sex, race, and ethnicity) will be summarized by treatment group and overall using descriptive statistics for age, and using number and percentage of subjects for sex, race, and ethnicity. The summary of demographic data will be provided for the Safety Analysis Set.

A by-subject demographic listing, including the informed consent date, will be provided by subject ID number in ascending order.

5.2. Baseline Characteristics

The baseline characteristics include:

- weight (kg)
- body mass index (BMI; in kg/m²)
- CLE disease subtype (CCLE, SCLE)
- time from CLE diagnosis to enrollment (as continuous in years, < 10 and \geq 10 years)
- diagnosis of SLE (Yes, No)
- diagnosis of RA (Yes, No)
- diagnosis of Sjogren's Syndrome (Yes, No)
- concurrent background systemic DMARD use at baseline (Yes, No)
- concurrent background use of systemic (oral) corticosteroids (Yes, No)
- concurrent background use of anti-malarial DMARD drugs (Yes, No)

- baseline CLASI Activity score (as continuous variable, categories <15 and >=15)
- baseline CLASI Damage score (as continuous variable, categories < 10 and >=10)
- baseline subject's global assessment of CLE activity (mm)
- baseline physician's global assessment of CLE activity (mm)

The time from CLE diagnosis will be calculated in years between the date of enrollment and the date of diagnosis. The missing month will be imputed with January, the missing day will be imputed with 1st day of the month.

The baseline characteristics will be summarized by treatment group and overall using descriptive statistics (n, mean, SD, median, Q1, Q3, minimum, and maximum) for continuous variables and using number and percentage for categorical variables.

The summary of baseline characteristics will be provided for the FAS. No formal statistical testing is planned.

A by-subject listing of other baseline characteristics will be provided by subject ID number in ascending order.

5.3. Medical History

Medical history will be collected at screening for CLE and other conditions.

The medical history data will be coded using the Medical Dictionary for Regulatory Activities (MedDRA).

Medical history data will be summarized by system organ class (SOC), preferred term (PT), treatment group, and overall. Subjects who report 2 or more medical history items that are coded to the same SOC and/or PT will be counted only once by the unique coded term in the summary. The summary will be provided for the Safety Analysis Set. No formal statistical testing is planned.

The CLE-related medical history will be summarized by treatment group and overall by the number and percentage of subjects with each CLE subtype.

6. EFFICACY ANALYSES

Efficacy endpoints will be evaluated for the following treatment periods: Placebo controlled period up to Week 12 and the entire study up to Week 48.

For the binary variables, non-responder imputation will be used. For continuous variables, imputation will not be performed prior to MMRM analysis.

The primary endpoint will be analyzed based on the estimands presented in [Table 4](#).

Table 4.

Continuous Endpoint	Treatment Policy	Hypothetical
Population	FAS	FAS
Endpoint	Change from Baseline	Change from Baseline
Intercurrent Event	Ignore all intercurrent events	
• Treatment discontinuation• Start of prohibited medication• The dose change of medication that required to be stable 
Treat data as missing after the event.

Estimator	MMRM with no imputation of missing data	MMRM with no imputation of missing data

6.1. Definition of the Primary Efficacy Endpoints

The primary efficacy endpoint for this study is the change in CLASI activity score from baseline to Week 12.

Activity score is the sum of the scores of the left side of the CLASI worksheet (i.e. for erythema, scale/hypertrophy, mucous membrane involvement and alopecia. See [Appendix 2](#)). The activity score ranges from 0 to 70 with higher score indicating more severe skin disease.

6.2. Analysis of the Primary Efficacy Endpoint

The primary analyses will be a test of superiority with the null hypotheses below:

- H01: There is no difference between filgotinib 200 mg and placebo in the change in CLASI activity score from baseline to Week 12
- H02: There is no difference between lanraplenib 30 mg and placebo in the change in CLASI activity score from baseline to Week 12

The primary endpoint will be analyzed using a mixed-effects repeated measures (MMRM) model. The model may include terms for baseline CLASI-A value, treatment, stratification factors (disease subtype, and concurrent background DMARD use), visit, and treatment-by-visit

interaction. Subject will be included as a random effect. The Kenward-Roger method will be used to estimate the degrees of freedom. The two treatment comparisons versus placebo will be done separately at the 2-sided 0.1 level. The unstructured (UN) variance-covariance matrix of repeated measures will be considered first. If model does not converge then ARH(1) structure will be applied.

The primary analysis will be based on the treatment policy estimand. The described analysis is the main estimator for the primary endpoint.

Descriptive statistics (n, mean, SD, median, Q1, Q3, minimum, and maximum) will be presented in the descriptive summaries. Adjusted means and 95% confidence intervals (CIs) will also be provided for each visit and treatment group.

Descriptive statistics of change from baseline in CLASI-A at Week 12 will be presented for the subgroups specified in Section 3.4.

The line plots for median (Q1, Q3) change (absolute and percent) in CLASI-A from baseline, mean (+/- 95% CI) change from baseline, and the adjusted estimates of mean change from baseline (+/- 95% CI) will be provided.

A plot of cumulative distribution of change from baseline in CLASI-A at Week 12 will be presented by treatment group on the observed data.

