8.5. Efficacy Analysis

8.5.1. Primary Analysis

The primary endpoint is the change in CLASI activity score from baseline to Week 12. The primary analysis will consist of superiority test of filgotinib 200 mg versus placebo and GS-9876 30 mg versus placebo, respectively. The primary endpoint will be analyzed using a mixed-effect repeated measures (MMRM) model. The model may include terms for baseline CLASI value, treatment, visit, and treatment-by-visit interaction. Subjects will be included as a random effect.

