6.3. Sensitivity Analysis of Primary Endpoint

The following sensitivity analyses of the primary endpoint (Change in CLASI-A total score at Week 12) will be performed:

- primary analysis repeated on hypothetical estimand
- non-parametric ANCOVA analysis using rank transformed data

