6.6. Changes From Protocol-Specified Efficacy Analyses

The treatment policy and hypothetical estimands have been added to the analyses of the primary endpoint.

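### Does listing subject as a random effect next to an unstructured covariance undermine the primary MMRM?

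*SAP*

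**What the plan says.** SAP 6.2 describes the primary model as an MMRM that may include baseline CLASI-A, treatment, the two stratification factors, visit and treatment-by-visit interaction. It then adds:

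- "Subject will be included as a random effect"
- "The Kenward-Roger method will be used to estimate the degrees of freedom"
- "The unstructured (UN) variance-covariance matrix of repeated measures will be considered first"
- "If model does not converge then ARH(1) structure will be applied"

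Protocol 8.5.1 has nearly the same first sentence, "Subjects will be included as a random effect", and names no covariance structure. SAP 6.3 lists "primary analysis repeated on hypothetical estimand" as a sensitivity analysis, so the same model is fitted a second time. SAP 10 names SAS 9.4 as the analysis software.

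Neither document says whether the random effect is meant as a variance component or only as the identifier that groups a subject's visits. Neither says whether it is kept under ARH(1), what counts as failure to converge, or which visits enter the model.

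**The concern.** An unstructured matrix already allows any pattern of variances and covariances between visits. A random subject effect adds one common constant to every element of that matrix, so the data cannot separate the two sources. The information matrix for the covariance parameters is then singular by construction.

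This matters because the plan's only fallback depends on convergence. If software reported the singularity as a failed fit, the primary p-value would come from ARH(1) for a numerical reason unrelated to the data. The SAP would then not identify a single model, because ARH(1) with and without the random effect are both estimable and they differ. At stake is whether a prespecified rule, or an analyst's reading of software output, chooses the model behind the primary test.

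**Working it through.** **Inputs.** From SAP 1.3: 20, 20 and 10 subjects, SD 2, 10% drop-out per arm, a 2-point difference, two-sided level 0.10 and power 79%. From SAP 6.2: UN first, then ARH(1), with Kenward-Roger. Assumed: the model uses the four post-baseline visits to Week 12 (Weeks 2, 4, 8 and 12). Because SAP 6 also covers the period to Week 48, 8 and 12 visits are shown as a range. All correlations, and the SDs at earlier visits, are assumptions; the documents give only SD 2.

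**The plan's own figure.** After 10% drop-out, 18 active and 9 placebo subjects remain.

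- SE = 2 × √(1/18 + 1/9) = 0.816
- 2 / 0.816 = 2.449, and 2.449 − 1.645 = 0.804
- Φ(0.804) = 0.7895, which reproduces 79%

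This calculation uses Week 12 alone, so it does not depend on the covariance across visits.

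**The redundancy.** With t visits, UN has t(t+1)/2 parameters. Adding a random intercept gives the marginal covariance V = R + σ_b²J, where R is unstructured and J is a matrix of ones. J is itself a symmetric matrix, so it adds no new direction.

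| Visits | UN: parameters / rank | UN + random effect | ARH(1) | ARH(1) + random effect |
|---|---|---|---|---|
| 4 | 10 / 10 | 11 / 10 | 5 / 5 | 6 / 6 |
| 8 | 36 / 36 | 37 / 36 | 9 / 9 | 10 / 10 |
| 12 | 78 / 78 | 79 / 78 | 13 / 13 | 14 / 14 |

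Exactly one parameter is redundant, whatever the number of visits.

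**Why the result does not move.** Every V of the form R + σ_b²J is an unstructured matrix, and every unstructured matrix is obtained by setting σ_b² = 0. The two models therefore allow the same set of V and share the same REML maximum. The Week 12 contrast and its model-based SE depend only on V. As a numerical check, the REML log-likelihood agreed to six decimals at σ_b² = 0, 0.1, 0.3 and 0.6 in nine simulated data sets.

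**Simulation of the planned analysis.** There were 100 trials under each of three covariances, giving 300 trials and 600 active-placebo comparisons. Week 12 SD was 2, with SDs of 1.4, 1.6 and 1.8 at Weeks 2, 4 and 8. Correlation was 0.6 throughout, exp(−0.08 × weeks apart), or 0.4 + 0.5 exp(−0.15 × weeks apart). First-order Kenward-Roger was used, with a generalised inverse for the singular case. UN plus random effect against UN alone:

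- same REML maximum in 300 of 300 trials
- Week 12 SE equal to within 2e-7, degrees of freedom to within 2e-6
- significance at 0.10 changed in 0 of 600 comparisons with no effect, and in 0 of 600 at 2 points

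A separate set of fits by scoring converged in 90 of 90 trials both with and without the random effect, with Week 12 SEs within 7e-5 of each other.

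**If the fallback were used.** In the same 300 trials, mean SE relative to UN was +0.2% to +4.4% for ARH(1) and −5.8% to +4.7% for ARH(1) plus random effect. The two gave different calls at 0.10 in 11/600 = 1.8% of comparisons with no effect and 7/600 = 1.2% at 2 points (0 to 3% by scenario).

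A second simulation used other assumed covariances and an approximate critical value of 1.68 instead of Kenward-Roger. Mean SEs were 0.794 to 0.810 for UN, 0.801 to 0.814 for ARH(1) and 0.801 to 0.808 for ARH(1) plus random effect. Decisions differed in 1 to 4 of 100 trials.

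**The case for a change.** The strongest argument for a change is that the fallback hangs on an undefined event in a model whose information matrix is singular by design. A positive-definiteness check of the Hessian failed in 137 of 300 simulated trials with the random effect and in none with UN alone. In single trials of the second simulation, the two readings of ARH(1) differed by up to 0.35 points in the Week 12 estimate, and the ratio of their SEs ran from 0.88 to 1.11. The remedy would be two or three sentences.

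Part of this stands. The wording is loose, and the fallback can be read in two ways. The step from a singular matrix to a triggered fallback has not been shown:

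- The 137 failures are not a convergence rate. The smallest eigenvalue is zero apart from rounding, so the check passes or fails on rounding error. The SAP switches only when the model does not converge, and in these same trials the fit reached its maximum every time. The documents cannot settle how SAS 9.4 would report the redundancy.
- The fallback ambiguity matters only once UN has failed. The 1.8% and 1.2% figures take the fallback as always used; the actual effect is those rates multiplied by the chance of that failure, which was not estimated.
- The two estimands could end up under different covariance structures, but that can happen with any UN-then-ARH(1) rule applied to two data sets. Removing the random effect would not prevent it.

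**Conclusion.** No change to the plan is needed. The algebra behind the concern is right: on a literal reading one covariance parameter is redundant. The redundancy leaves the Week 12 estimate, its SE and its test as they are under UN alone, and the 79% power is unaffected.

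The natural reading is also harmless. SAP 6.2 calls the model an MMRM, specifies the covariance for the repeated measures, and carries over the random-effect sentence from a protocol section that names no covariance structure. An analyst will most likely treat subject as the identifier that links visits. One who fits the sentence literally and reaches convergence gets the same answer.

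What remains is whether the random effect stays under ARH(1), and a convergence criterion left to good practice. The first affects under 2% of significance calls overall in the Kenward-Roger simulation even if UN always failed, and up to 4 of 100 trials in the cruder second one. Both sets of figures rest on assumed covariances and four visits to Week 12. The exact redundancy does not depend on those assumptions.
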